3.4 RESPONSE/SURVIVAL FOLLOW-UP PERIOD

Subjects who do not experience progressive disease prior to treatment discontinuation will continue to have radiologic and clinical tumor assessments every 9 weeks for the first year and every 12 weeks during the second year until progression is confirmed, consent withdrawal, start of a new anti-cancer treatment, loss to follow-up, or death, whichever comes first. These subjects will also be followed by telephone every 12 weeks during the second year. The duration for response/survival follow-up is approximately 2 years from the first dose of study drug.

4 STATISTICAL CONSIDERATIONS

4.1 GENERAL CONSIDERATIONS

The below conventions will be used:

- Continuous variables will be summarized using descriptive statistics namely the sample size (n), mean, standard deviation (SD), median, minimum (min) and maximum (max). Mean and median will be rounded to one more decimal place than the original data (up to 3 decimals). Standard deviation will be rounded to two more decimal places than the original data. Minimum and maximum will have the same decimal place as the original data.
- Categorical variables will be summarized using counts and percentages with 2-sided 95% confidence intervals (CIs) where appropriate. Percentages will be rounded to 1 decimal place.
- As Part 2 of the study was not initiated due to an insufficient number of clinical responses observed in Part 1, summary tables and data listings will only be presented for Part 1. Summary tables will be presented by cohort and overall, and data listings will be presented by cohort and subject.

4.2 SAMPLE SIZE DETERMINATION

For Part 1 of the study, the sample size is not based on formal statistical considerations. Rather, it is based on a desire to obtain sufficient safety, tolerability, pharmacokinetic, pharmacodynamic, and preliminary efficacy information while exposing as few patients as possible to the investigational treatment. With up to 30 patients per cohort, Part 1 of the study provides an opportunity to further investigate the safety profile and explore tumor activities in a more selective patient population and helps to make decision for the Part 2 design.

4.3 BASELINE AND STUDY DAY DEFINITIONS

4.3.1 Baseline Definition

Baseline is defined as the last non-missing measurement prior to the first dose of study drug. If multiple values are present for the same time point (same date if time is absent,

or same datetime), the average of the non-missing values will be used as the baseline. If there is no non-missing measurement prior to the first dose, the baseline value will not be imputed and will remain missing.

4.3.2 Study Day

Study day will be calculated to show the day of an event relative to the reference start date.

The reference start date (Day 1) is defined as the first dose day of the study treatment.

- Study day = (event date – reference start date +1) if the event date is on or after the reference start date
- Study day = (event date – reference start date) if the event date is prior to the reference start date

There is no study day 0. The study day will be missing when the event date is missing or incomplete.

4.4 ANALYSIS VISIT WINDOWS

Analysis visit windows will not be used for this study.

4.5 HANDLING OF MISSING AND INCOMPLETE DATA

Missing/incomplete data will not be imputed unless otherwise specified.

4.5.1 Dates Imputation Rules

Missing/incomplete start date of subsequent anti-tumor therapies (the earliest start date of subsequent systemic therapies, radiotherapies or surgeries/procedures) will be imputed as follows:

- If day is missing, use the date of the last dose of study drug + 1 day if it is in the same year and month as the available partial date; otherwise use day 1 of the month.
- If month and day are both missing, use the date of the last dose of study drug + 1 day if it is in the same year as the available partial date; otherwise use January 1st.
- If the date is completely missing, use the date of the last dose of study drug + 1 day.

Missing/incomplete adverse event start dates will be imputed as follows:

- If day is missing, use the first dose date of the study treatment if it is in the same year and month as the available partial date; otherwise use day 1 of the month.

- If month and day are both missing, use the first dose date of the study treatment if it is in the same year as the available partial date; otherwise use January 1st of the year.
- If the date is completely missing, no imputation will be applied.

A missing/incomplete death date will be imputed as the complete last date known to be alive +1 day, day 1 of the month if only missing day or January 1st if missing day and month, whichever occurs last.

A missing/incomplete last alive date will be imputed to be the death date if a complete death date is available; otherwise the last alive date will be derived from the last available visit/assessment date.

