### 8.4.1 Adverse Event Reporting Time Period

All AEs, whether reported by the subject voluntarily or upon questioning, or noted on physical examination, will be recorded from the time the ICF is signed until study completion, 30 days after the last dose of study drug or 30 days following cessation of study treatment if the subject initiates new anti-cancer therapy, whichever is earlier. The event name, date of onset, duration, and severity will be documented, together with an Investigator's (or designee's) opinion of the relationship to study drug.

**Before initiation of study drug**, only the AEs which regarded as have relationship to study procedure will be collected as AE.

All SAEs (regardless of relationship to study drug) and/or non-serious AE considered to be possibly, probably or definitely related to study drug recorded during the course of the study will be followed up, where possible, until resolution or until the unresolved AEs are judged by the Investigator (or designee) to have stabilized. This will be completed at the Investigator's (or designee's) discretion. Medical occurrences that begin before the start of study drug, but after obtaining informed consent, will be recorded on the Medical History/Current Medical Conditions section of the eCRF rather than in the Adverse Event section.

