9.1 ADVERSE EVENTS

Adverse events (AEs) will be coded to the system organ class (SOC) and preferred term (PT) using MedDRA version 25.1. Toxicity grading is based on the National Cancer Institute Common Terminology Criteria for Adverse Events (NCI CTCAE) version 5.0.

All AE summaries will be limited to the treatment-emergent adverse events (TEAEs). A TEAE is defined as an AE that has an onset or a worsening in severity during or after the first dose of study drug and up to 30 days after the last dose of study drug, or one day prior to the subsequent anti-tumor therapy, whichever occurs earlier. An AE that has a change in severity will be recorded as two separate AEs on the CRF under the same SOC/PT of different severity levels. If an AE has a missing onset date, it will be considered as a TEAE in the below situations:

- An AE whose onset date and end date are both missing.
- An AE where the onset date is missing and the end date is after the first dose date of study drug
- An AE where the onset date is missing, the end date is on the first dose date of study drug, and the end time (hh:mm) is absent or after the initiation of the first dose of study drug.

An overall summary of TEAEs will be presented to include the number and percentage of subjects with at least 1 TEAE in the following categories:

- Any TEAE
- Serious TEAE
- TEAE of CTCAE grade ≥ 3
- TEAE of maximum CTCAE Grade 3
- TEAE of maximum CTCAE Grade 4
- TEAE of maximum CTCAE Grade 5
- Infusion-related reaction
- TEAE related to any study drug
- TEAE related to TJ004309
- TEAE related to atezolizumab
- Serious TEAE related to any study drug
- Serious TEAE related to TJ004309

- Serious TEAE related to atezolizumab
- TEAE of CTCAE grade ≥ 3 related to any study drug
- TEAE of CTCAE grade ≥ 3 related to TJ004309
- TEAE of CTCAE grade ≥ 3 related to atezolizumab
- TEAE leading to any study drug discontinuation
- TEAE leading to TJ004309 discontinuation
- TEAE leading to atezolizumab discontinuation
- TEAE leading to death

In addition, the number and percentage of subjects with at least one TEAE in the following categories will be summarized by SOC and PT (unless noted otherwise below) for each cohort and overall:

- Any TEAE (summarized by SOC, PT and maximum CTCAE grade)
- Serious TEAE
- TEAE of CTCAE grade ≥ 3 (summarized by SOC, PT and maximum CTCAE grade)
- TEAE of CTCAE grade ≥ 3 related to any study drug (summarized by SOC, PT and maximum CTCAE grade)

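### SAP 4.5.1 moves a partial AE start date to the first-dose date without checking the AE end date, so a screening AE that ended before dosing can be counted as treatment-emergent

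*SAP*

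**What the plan says.** SAP 4.5.1 has three rules for AE start dates.

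- Day unknown: "If day is missing, use the first dose date of the study treatment if it is in the same year and month" as the partial date; otherwise the first of the month.
- Day and month unknown: "If month and day are both missing, use the first dose date of the study treatment if it is in the same year"; otherwise 1 January.
- Nothing known: "If the date is completely missing, no imputation will be applied".

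None of the three mentions the AE end date.

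SAP 9.1 then classifies the record: "A TEAE is defined as an AE that has an onset or a worsening in severity during or after the first dose of study drug", within a window that closes 30 days after the last dose or the day before subsequent anti-tumor therapy, whichever is earlier. For records with a missing onset date, SAP 9.1 lists when they count as treatment-emergent. Apart from the case where both dates are missing, the test is the end date, for example: "An AE where the onset date is missing and the end date is after the first dose date of study drug".

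On AEs before dosing, Protocol 8.4.1 says that "only the AEs which regarded as have relationship to study procedure will be collected as AE"; other occurrences between consent and first dose go to the medical history page. Protocol 8.3.1 names screening biopsies as a source of such procedure-related AEs, and the schedule of assessments (Protocol Table 2) has AE recording at Screening.

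**The concern.** Moving an uncertain start to the first-dose date is a normal conservative convention when the event might have begun on treatment. It is not conservative when the end date shows that the event was over before the first infusion. Its timing relative to dosing is then known, and the imputation overrides what the record says.

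The two SAP sections also treat the same event in opposite ways. With no start date at all, the end date decides and the event is left out. Once the month or year is known, the end date is ignored and the event is counted. More information leads to the worse classification.

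What is at stake is the treatment-emergent AE tables. A harm from a screening procedure, before any study drug, would appear in them. If the causality or grade of that record were also missing, SAP 9.1 would set it to related or to Grade 3, and the event would reach those tables too.

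**Working it through.** The documents give no figure on this point, so there is none to reproduce. The check applies the rules of SAP 4.5.1 and 9.1 literally to test records. The dates are assumed for illustration: first dose 15 March 2022, last dose 1 June 2022.

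| Recorded start | Recorded end | Start after SAP 4.5.1 | Start after end? | Treatment-emergent as written | With an end-date check |
|---|---|---|---|---|---|
| March 2022, day unknown | 10 March | 15 March | yes | yes | no |
| 2022 only | 25 February | 15 March | yes | yes | no |
| completely missing | 10 March | none | – | no | no |
| March 2022, day unknown | 20 March | 15 March | no | yes | yes |
| February 2022, day unknown | 20 March | 1 February | no | no | no |

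Rows 1 and 2 are the error: both events ended before dosing, both get an impossible start, and both are counted. Row 3 is the row 1 event with less information, and it is classified correctly. Row 4 is truly uncertain; counting it is reasonable, and the end-date check leaves it counted.

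**Size of one misclassification.** SAP 3.1 allows up to 30 subjects per cohort, so up to 60 overall, and SAP 4.1 presents tables by cohort and overall. SAP 9.1 counts each subject once per category. If a subject has no other event in the category, one wrong record adds 100/30 = 3.3 percentage points in a full cohort or 100/60 = 1.7 points overall. A cohort that stopped at the 15-subject futility look would give 100/15 = 6.7 points.

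**How often the month can match.** Screening lasts at most 28 days (Protocol Table 2). Assume that first-dose days are spread evenly over a month of L days. A first dose on day d has min(d − 1, 28) screening days in its own month, so the mean share is the sum of min(d − 1, 28) over d = 1 to L, divided by 28 × L:

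- L = 28: 378/784 = 48%
- L = 30: 434/840 = 52%
- L = 31: 462/868 = 53%

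This is the share of screening days on which a day-unknown onset would meet the month condition. It is not an error rate: the record must also have a partial start and an end before first dose, and the documents give no frequency for either.

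**The case against.** The strongest reply is that the affected set is tiny and may be empty. An error needs all of these together: a procedure-related AE before dosing, an unknown start day, an end date good enough to show that the event was over, and a match with the month or year of first dose. Protocol 8.4.1 requires the onset date to be documented, and a year-only onset for an event within a 28-day screening period is unlikely. Fresh biopsies are planned only in Cohort 2, from at least 5 patients. Protocol 8.4.3 obliges the investigator to assess causality, so the default to related would seldom apply. The safety analysis is descriptive and the error runs towards over-counting. AEs are also listed by subject, so a start after its end could be noticed if imputed dates are shown. All of this stands and keeps the point minor. It does not make the rule right: a listing exposes the problem but does not correct the tables.

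Three stronger readings are tempting, and the documents do not support them.

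- A reader might infer that an AE whose grade falls after dosing becomes a new treatment-emergent event. SAP 9.1 says "An AE that has a change in severity will be recorded as two separate AEs on the CRF" and does not limit this to worsening, but it gives the second record no new onset, and its definition counts only an onset or a worsening. A Grade 3 event from before dosing that improves to Grade 1 afterwards could be miscounted only if a programmer took the second record's start as an onset. That is an ambiguity, not a stated rule.
- A reader might infer that partially dated events ending after first dose are also misclassified. They are not; counting them is ordinary conservative handling.
- A reader might take the 48% to 53% above as the proportion misclassified. It describes one of several necessary conditions.

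**Conclusion.** The point holds for partial start dates. As written, SAP 4.5.1 classifies as treatment-emergent any AE whose partial start matches the month or year of first dose, even when the recorded end precedes that dose. This contradicts the use of the end date in SAP 9.1 for completely missing starts.

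The importance is low. The number of affected records cannot be estimated from the documents and may be zero. Each affected subject shifts a table entry by 3.3 points (N = 30) or 1.7 points (N = 60), assuming full enrollment and no other event for that subject in the same category. The objective response rate and the Cohort 1 futility rule do not depend on AE dates and are unaffected.

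**What to change.** Add to the AE start-date rules in SAP 4.5.1, for partial dates that match the month and year, or the year, of first dose:

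*Impute to the first-dose date only if the AE end date is missing, is on or after the first-dose date, or is partial and does not establish that the event ended before first dose. Otherwise impute to day 1 of the month (or 1 January), and the AE is not treatment-emergent unless it worsens after first dose.*

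The clause on partial end dates is needed because the SAP has no imputation rule for AE end dates. Partial starts in a month or year other than that of first dose keep their present rule. In the test records, the check corrects rows 1 and 2 and leaves the other three unchanged.

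Optionally, for clarity, add to SAP 9.1: *A second record opened for a decrease in grade is not a new onset and keeps the treatment-emergent status of the record it continues.* The end-date check does not settle that case, so it needs its own sentence.

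The cost is one SAP sentence pair, one optional sentence and a small change to the derivation program. No new data are needed.

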4.6 ANALYSIS SOFTWARE

SAS® Enterprise Guide 8.2 will be used for data analysis and reporting.

5 PROTOCOL DEVIATIONS

Protocol deviations will be listed by subject for the safety analysis set.

6 STUDY SUBJECTS

The safety analysis set will be used for the summary tables and data listings in this section unless specified otherwise.

6.1 SUBJECT DISPOSITION

The number and percentage of enrolled subjects in each of the following categories will be summarized:

- Subjects enrolled
- Subjects who received any dose of treatment
- Subjects who did not receive any dose of treatment
- Subjects who discontinued treatment and reasons
- Subjects who completed the study
- Subjects who withdrew early from the study and reasons

Subject disposition information will be listed by subject for the safety analysis set.

6.2 ANALYSIS SETS

The following analysis sets are defined:

Analysis set	Definition
Safety analysis set	All subjects who receive at least 1 dose of study drug
Efficacy evaluable analysis set	All subjects who receive at least 1 dose of study drug and undergo at least 1 post-baseline tumor assessment. Subjects who die before the first scheduled post-baseline tumor assessment will be included in this evaluable set.

The number and percentage of enrolled subjects in each analysis set will be summarized.

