#### 9.2.1 Disposition

The number of patients included in each analysis set will be summarized, along with the reason for any exclusions. Patients discontinuing from study treatment and/or withdrawing from study participation the primary reason for discontinuation will be summarized.

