### 9.2.4 Efficacy Analyses

A listing of tumor measurements will be provided by subject and time. BOR, ORR, DOR, PFS and OS will be listed and summarized by cohort/group based on efficacy evaluable population if data permits.

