8 EFFICACY ANALYSIS

The efficacy evaluable analysis set will be used for the efficacy summary.

The anti-tumor efficacy of the combination of TJ004309 and atezolizumab will be summarized by best of response (BOR) and objective response rate (ORR) assessed by the Response Evaluation Criteria in Solid Tumors (RECIST 1.1) and immune RECIST (iRECIST) guidelines. All tumor response data (including unscheduled tumor assessments) will be used in the efficacy analysis.

Efficacy endpoints such as duration of response (DOR), progression-free survival (PFS) and overall survival (OS) will not be reported due to the abbreviated nature of the CSR to be produced.

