8.3 PRESENTATION

The efficacy summary will include the following:

- Number and percentage of subjects who died before the first response assessment
- Number and percentage of subjects who had at least one response assessment per RECIST 1.1
- Number and percentage of each response (i.e. CR, PR, SD, PD, NE) as the best overall response per RECIST 1.1
- Observed objective response rate (per RECIST 1.1) and the 95% Clopper-Pearson confidence interval
- Number and percentage of subjects who had at least one response assessment per iRECIST
- Number and percentage of each response (i.e. iCR, iPR, iSD, iUPD, iCPD, NE) as the best overall response per iRECIST
- Observed objective response rate (per iRECIST) and the 95% Clopper-Pearson confidence interval

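### The primary ORR is planned only on the efficacy-evaluable set; no supportive all-treated ORR is planned, although treated subjects without a scan can leave the denominator (minor, cheap to fix)

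*SAP*

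**What the plan says.** ORR by RECIST 1.1 is the primary endpoint (protocol 3.2.1, SAP 2.2.1). SAP 6.2 defines the efficacy-evaluable set as "All subjects who receive at least 1 dose of study drug and undergo at least 1 post-baseline tumor assessment" and makes one exception: "Subjects who die before the first scheduled post-baseline tumor assessment will be included in this evaluable set". SAP 8 then states: "The efficacy evaluable analysis set will be used for the efficacy summary". Protocol 9.2.4 agrees: "BOR, ORR, DOR, PFS and OS will be listed and summarized by cohort/group based on efficacy evaluable population if data permits". The set definition is also the same in substance in the protocol synopsis and protocol 9.1.

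The planned RECIST output in SAP 8.3 is "Observed objective response rate (per RECIST 1.1) and the 95% Clopper-Pearson confidence interval", with a matching line for iRECIST. The safety analysis set (every subject dosed) is assigned to SAP sections 6, 7 and 9 but not to section 8. SAP 4.5 imputes no missing data unless specified, and no rule counts an unscanned subject outside the evaluable set as a non-responder.

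On exclusions, protocol 9.2.1 plans this: "The number of patients included in each analysis set will be summarized, along with the reason for any exclusions". SAP 6.2 carries over the number and percentage in each set but not the reasons. SAP 6.1 tabulates reasons for stopping treatment and "Subjects who withdrew early from the study and reasons".

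**The concern.** A BOR of CR or PR requires at least one post-baseline assessment (SAP 8.1). A treated subject with no such assessment can therefore never enter the numerator. The plan keeps some of these subjects as non-responders (deaths before the first scheduled assessment) and removes the rest:

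- those who leave alive and unscanned, for example through consent withdrawal, new anti-cancer treatment or loss to follow-up, each of which ends response imaging under SAP 3.4;
- those who die unscanned after the first scheduled assessment.

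The first scheduled assessment is Cycle 4 Day 1 (protocol Table 2, footnote u), nominally week 9. Eligibility asks for a life expectancy of 12 weeks or more (protocol 5.1, criterion 11), so some subjects could worsen and leave before that scan.

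Removing only subjects who cannot respond moves the result in one direction. Part 1 has no control arm, and SAP 8 drops DOR, PFS and OS from the report. The response rate and its interval therefore carry the efficacy result, and no planned output shows them for everyone treated.

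**Working it through.** **Inputs from the documents.** Up to 30 subjects per cohort (SAP 3.1). A futility look in Cohort 1 at 15 (protocol 9.3). A 95% Clopper-Pearson interval (SAP 8.3). First scheduled scan at Cycle 4 Day 1, which is 3 × 21 days = 63 days, or 9 weeks, after the first dose. There is no formal sample-size basis (SAP 4.2), so there is no design figure for ORR to reproduce.

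**Inputs assumed.** Let N be the number treated, r the number of responders, and d the number treated, unscanned and not added back. The documents give neither r nor d. I use d = 1 to 6 for N = 30. I also use d = 1 to 3 for a cohort that ends at N = 15; that end point is an assumption too. d = 0 is possible.

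**Formulas.**

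- All-treated ORR = r/N; evaluable-set ORR = r/(N-d).
- Ratio = N/(N-d): 30/29 = 1.03, 30/27 = 1.11, 30/24 = 1.25; 15/14 = 1.07, 15/12 = 1.25.
- Clopper-Pearson limits with n the denominator: lower = 2.5% quantile of Beta(r, n-r+1); upper = 97.5% quantile of Beta(r+1, n-r). For r = 0 the lower limit is 0 and the upper is 1 - 0.025^(1/n).

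**Results, % (95% CI).**

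| N | r | d = 0 (all treated) | d = 1 | d = 3 | d = 6 |
|---|---|---|---|---|---|
| 30 | 0 | 0 (0-11.6) | 0 (0-11.9) | 0 (0-12.8) | 0 (0-14.2) |
| 30 | 1 | 3.3 (0.1-17.2) | 3.4 (0.1-17.8) | 3.7 (0.1-19.0) | 4.2 (0.1-21.1) |
| 30 | 3 | 10.0 (2.1-26.5) | 10.3 (2.2-27.4) | 11.1 (2.4-29.2) | 12.5 (2.7-32.4) |
| 15 | 0 | 0 (0-21.8) | 0 (0-23.2) | 0 (0-26.5) | not used |
| 15 | 2 | 13.3 (1.7-40.5) | 14.3 (1.8-42.8) | 16.7 (2.1-48.4) | not used |

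**Reading.** For 3 of 30 the estimate moves by 10.3 - 10.0 = 0.3 points at d = 1 and 12.5 - 10.0 = 2.5 points at d = 6. The all-treated interval is 26.5 - 2.1 = 24.4 points wide. With no responders the estimate does not move; the upper limit for N = 30 rises by 0.3 points (11.6 to 11.9, rounded values) at d = 1 and 2.6 points (11.6 to 14.2) at d = 6. With d = 0 the two analyses are identical.

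**The case against.** The strongest reply is that this is a choice of denominator, made in advance and stated consistently in protocol and SAP. The upward shift exists only relative to an all-treated rate, which the documents do not adopt. Early deaths stay in as non-responders, and so do scanned subjects whose BOR is NE. SAP 6.2 prints the size of each set, so a reader can divide responders by the number treated and work out an exact interval. No source gives d, and Appendix 1 of the protocol asks sites to make every effort to document progression after treatment stops, which should keep d down. Part 2 was not initiated because responses were too few (SAP 4.1); an all-treated rate could only be equal or lower, so it could not reverse that decision.

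All of this stands, and it limits the weight of the point. It does not remove it, because the all-treated rate and interval are still not a planned output.

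Some stronger readings are tempting but not supported:

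- *That stopping study drug excludes a subject.* It does not in itself. Imaging continues off treatment for subjects without progression (SAP 3.4), and unscheduled scans count (SAP 8).
- *That SAP 8.3 contradicts SAP 6.2 on deaths.* The 8.3 row is "Number and percentage of subjects who died before the first response assessment", without the word scheduled. But that row is tabulated inside the evaluable set, where subjects who died unscanned after the first scheduled assessment are already absent.
- *That dose delays widen the gap.* If Cycle 4 Day 1 moves later, more deaths fall before the first scheduled assessment and are added back. For late deaths this narrows the gap, if anything.
- *That replacement of subjects (protocol 7.2) removes more from the denominator.* Neither set definition drops a dosed subject because of replacement.
- *That the SAP abandoned the reasons for exclusion.* Protocol 9.2.1 still plans them; the SAP only fails to repeat them.

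**Conclusion.** The point holds as a minor one. The primary ORR is planned only on a set that can omit treated subjects who cannot be responders, and no all-treated ORR or interval is planned beside it. The direction is certain whenever d is above 0: a higher rate if there is any responder, and otherwise an unchanged 0% with a higher upper limit.

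The size is unknown because the documents do not give d. Over the assumed ranges the factor is 1.03 to 1.25 for 30 treated and 1.07 to 1.25 for 15 treated, which is small against the exact intervals at these sample sizes. A reader might infer that the efficacy conclusion is unsafe. The documents do not support that: no formal test or external benchmark is stated, and the decision on Part 2 would not change.

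**What to change.** In SAP 8 and 8.3, keep the prespecified evaluable-set result and add beside it a supportive ORR and iORR with 95% Clopper-Pearson intervals on the safety analysis set, by cohort. Count each treated subject without a post-baseline assessment as NE, and so as a non-responder. Label the analysis as added after responses were known, since SAP 4.1 shows that they were.

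In SAP 6.2, report the reasons for exclusion from each set, as protocol 9.2.1 already plans.

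The cost is a few lines of SAP text and one more column in the efficacy table; the safety set and the NE category already exist. The downside is a possibly slightly lower rate and two rates to explain. If nobody was excluded, the columns coincide and the report can say so.
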